6.1.4 Mycological Diagnosis

Mycological diagnosis of candidemia and/or invasive candidiasis sufficient for inclusion in the study will be established by one of the following test results from a blood sample or normally sterile site collected ≤ 4 days (96 hours) before randomization:

- ≥ 1 blood culture positive for yeast or *Candida*
- sponsor-approved rapid in vitro diagnostic (IVD) (e.g., T2Candida Panel, Septifast) test positive for *Candida* spp.
- a positive gram stain (or other method of direct microscopy) for yeast or positive culture for *Candida* spp. from a specimen obtained from a normally sterile site

Note: If the positive blood culture used to qualify the subject for the study is drawn >12 hours prior to randomization, an additional set of blood cultures must be obtained ≤ 12 hours before randomization to determine which subjects are still candidemic at enrollment. Results of the blood cultures obtained ≤ 12 hours before randomization are not required prior to randomization.

The dose and duration of any prior antifungal treatment received ≤ 4 weeks before randomization will be recorded at Screening.

For diagnosis of invasive candidiasis, cultures should be obtained from purulent fluid or necrotic tissues from normally sterile sites. Drainage tubes following invasive procedures may only be used to acquire fluid for culture for up to 24 hours following placement of the tube (after 24 hours tubes could be colonized with non-infecting pathogens). While potentially indicative of disease, a urine culture alone may not be used as the qualifying culture for entry into the study, though the presence of a positive urine culture is not a reason to exclude a patient from participation. Additionally, a respiratory tract specimen would not be considered sufficient to prove invasive candidiasis as these specimens are rarely sterile and pulmonary infection with *Candida* spp. is extremely rare.

Every reasonable effort must be made for source control of the *Candida* infection to properly evaluate the efficacy of study drug. Central catheters should be removed within 48 hours after diagnosis with candidemia, consistent with IDSA and ESCMID guidelines. For subjects with invasive candidiasis, surgical drainage or debridement of potentially infected fluid collections or necrotic tissues should be performed.

6.1.5 Retinal Examination

A retinal examination for evidence of a *Candida* eye infection, including endophthalmitis or chorioretinitis, should be performed on all subjects with candidemia during Screening when possible, although the exam may occur as late as Day 7. Retinal examination is standard of care for subjects with candidemia and should be performed by an ophthalmologist, when available. The retinal examination should be repeated in subjects who were negative at baseline if the subject develops visual signs or symptoms of a *Candida* eye infection during the study. Additionally, any neutropenic subjects who recover their neutrophil counts during the study should have an additional retinal examination. Subjects who were negative at baseline and diagnosed with a *Candida* eye infection after initiating study drug must discontinue study drug (see Section 7.4.2) but may continue in the study at the Investigator's discretion; all subsequent antifungal drugs, interventions, and outcomes for endophthalmitis or chorioretinitis will be recorded.

6.1.6 Study Day Definition

Study Day 1 is defined as the first day of study drug administration. Subsequent study days are counted as the number of consecutive calendar days thereafter.

6.1.7 Efficacy Assessments

Efficacy assessments for all subjects occur on Day 5, Day 14 (± 1 day), Day 30 (-2 days), EOT (≤ 2 days of last dose), and the Follow-up visit (Days 52–59). Clinical cure, radiological cure (for qualifying invasive candidiasis subjects), and mycological eradication will be assessed on all efficacy assessment days. Survival status will be assessed at Day 30 (-2 days) and the Follow-up visit (Days 52–59). Subjects who complete Day 30 assessments on Day 28 or Day 29 (within the -2 days period) without further information thereafter will be considered alive at Day 30. For mycological response, the location of *Candida* infection determines how eradication will be demonstrated:

a. Subjects with ≥ 1 blood culture positive for yeast or *Candida*

Blood cultures for efficacy following the first dose of study drug will be performed until the first negative blood culture result for *Candida* spp. with no subsequent positive culture (in cases when one or more samples are drawn and cultured after the first negative culture is available). Blood samples for cultures should be drawn daily when possible although may be drawn every other day until blood cultures are negative. Generally, blood cultures should involve samples from 2 separate draws with ≥ 1 draw from a peripheral vein without an IV catheter.

b. Subjects with a positive culture for *Candida* spp. from a normally sterile site

Note: only applies when infected sites are accessible; fluid samples from drainage tubes may only be collected for up to 24 hours following placement of the tube. Culture specimens for efficacy following the first dose of study drug should be

collected from all normally sterile sites of baseline infection at least every other day until the first negative culture result for *Candida* spp. with no subsequent positive culture (in cases when one or more samples are drawn and cultured after the first negative culture is available). If access to the infected site is not possible, then mycological eradication will be determined based on clinical outcome (see [Table 8](#)). Any time there is a culture obtained from a normally sterile site, there should be a surgical procedure recorded in the Medical History or in Concomitant Procedures (depending upon the study interval during which the sample was obtained).

6.1.8 Safety Assessments

Safety monitoring data is collected throughout the study. Adverse events are collected from the time the informed consent document is signed through the Follow-up visit (Days 52–59). Vital signs will be measured at each study visit. A physical examination will be performed at the Screening, Day 5, Day 14 (± 1 day), Day 30 (-2 days), EOT (≤ 2 days of last dose), and Follow-up (Days 52–59) visits. Subjects will be assessed for signs and symptoms of tremor, ataxia, and peripheral neuropathy using a neurological exam at least at Screening and at EOT. More frequent neurological exams may be performed as directed by subject symptoms. Hematology and chemistry laboratory tests will be performed at the Screening, Day 1, Day 2, Day 4, Day 8 (± 1 day), Day 14 (± 1 day), Day 30 (-2 days), EOT (≤ 2 days of last dose), and Follow-up visits (Days 52–59). Urinalysis will be performed at the Screening and EOT (≤ 2 days of last dose) visits. Coagulation laboratory tests (Prothrombin Time or International Normalized Ratio [PT/INR]) will be performed at the Screening visit. An ECG will be performed at the Screening visit and on Day 1 at any time following administration of study drug (i.e., post-end IV infusion). An independent external DSMB will review safety data when approximately 50% of subjects are randomized in the study and as required for AESIs as provided in the DSMB Charter.

6.1.9 PK Sampling

Blood samples for PK analysis must be collected from the OPPOSITE arm of the infusion or through an arterial line during the infusion; after the infusion is complete, opposite arm or arterial line draws are preferred, but not mandatory. Blood samples will be collected as follows:

- Day 1: within 10 minutes before the end of infusion, and one sample taken any time between end of infusion and 12 hours after the end of infusion
- Days 2, 3, 4, or 5: One sample taken at any time on one day only
- Day 8: Pre-dose
- Day 14 (for subjects not receiving a Day 15 dose): One sample taken at any time
- Day 15: Pre-dose (if applicable)
- Day 22: Pre-dose (if applicable)

For subjects completing treatment on Day 14, a PK sample should be drawn at the same time as hematology and chemistry blood draws (i.e., random PK draw). **Note:** Pre-dose samples should be collected ≤ 30 minutes prior to the start of the infusion. For subjects receiving hemodialysis, an attempt should be made to obtain PK samples directly following hemodialysis if still within the required time window.

Blood samples will be collected from all subjects receiving study drug, although only PK samples from subjects receiving Rezafungin for Injection will be analyzed. PK sample analysis will be performed by an independent, central bioanalytical laboratory using a validated assay.

6.2 Number of Subjects

Approximately 218 subjects will be randomized to treatment (1:1, Rezafungin for Injection to caspofungin). The target of 218 subjects assumes approximately 85% of randomized subjects will be evaluable for the mITT population. Thus, 184 subjects will be in the mITT population (92 subjects in each treatment group). If the evaluability rate for the mITT population is higher than 85%, enrollment will be stopped when at least 184 randomized subjects have met the criteria to be included in the mITT population.

6.3 Measures Taken to Minimize Bias

Treatment assignment will be blinded to all blinded clinical site and sponsor personnel (double-blind) until the study database is locked. Unblinded personnel includes the site pharmacist preparing the infusions and the unblinded monitor to ensure study drug accountability and assignment throughout the trial as well as the Sponsor's unblinded team. Blinding is maintained with a double-dummy design wherein all subjects receive daily infusions until switched to oral step-down therapy. Subjects switched to oral step-down therapy receive daily oral therapy and weekly infusions.

6.4 Expected Duration of Subject Participation

Maximum study duration for an individual subject is 63 days, including Screening (≤ 4 days, 96 hours), the Required Treatment Period (Day 1 to Day 14 [14 days]), the Optional Extended Treatment Period (Day 15 to Day 28), and Follow-up (Days 52–59).

6.5 Method of Treatment Assignment and Blinding

After informed consent has been obtained, subjects will be screened for study eligibility before randomization.

Subjects will be randomly assigned (1:1 ratio) to receive either Rezafungin for Injection or caspofungin. Randomization will be stratified based on diagnosis (candidemia only; invasive candidiasis) and by Acute Physiology and Chronic Health Evaluation (APACHE II) score/ absolute neutrophil count (ANC) (APACHE II score ≥ 20 OR ANC < 500 cells/ μL ; APACHE II score < 20 AND ANC ≥ 500 cells/ μL) at Screening. If a subject has a positive result

for both blood culture/rapid IVD and culture specimen obtained from a normally sterile site, the subject will be randomized within the invasive candidiasis stratum.

The study site's pharmacist (or pharmacist designee) will obtain the study drug assignment via an Interactive Response Technology (IRT). Randomized subjects will be assigned the treatment corresponding to the next available randomization number from the computer-generated randomization schedule. A subject is considered randomized when a randomization transaction is recorded in the IRT.

All study personnel, including the Sponsor, Investigator, and site personnel involved in study conduct, and subjects will remain blinded to study medication assignment until the study is completed and the database is locked with the exception of the pharmacy monitor, unblinded project manager, clinical supplies, document manager, and quality (per the Sponsor Blinding Plan) who may be unblinded to study medication at any time during study conduct. The DSMB will be unblinded to safety data for periodic safety reviews as defined in the DSMB Charter. The Pharmacy Monitor will monitor study drug preparation and accountability during the study and cases in which unblinding is required due to a safety or tolerability issue. To maintain study blinding, study drug preparation will be performed by an unblinded site pharmacist (or qualified unblinded personnel at the study site not involved with study procedures or evaluations).

Instructions for study drug preparation and dosing are outlined in the Pharmacy Manual provided separately to the site. To maintain the blind, oral study drug pills must never be crushed. In the case of a medical emergency requiring the Investigator to know the identity of the study drug, the Investigator will follow the procedures outlined in [Section 8.4](#).

7.0 SELECTION, DISCONTINUATION, AND WITHDRAWAL OF SUBJECTS

7.1 Subject Inclusion Criteria

Subjects must meet ALL the following inclusion criteria to qualify for the study:

1. Willing and able to provide written informed consent. If the subject is unable to consent for himself/herself, a legally acceptable representative (i.e., acceptable to International Council on Harmonisation [ICH] and local law, as applicable) must provide informed consent on his/her behalf.
2. Males or females ≥ 18 years of age.
3. Established mycological diagnosis of candidemia and/or invasive candidiasis from a sample taken ≤ 4 days (96 hours) before randomization defined as:
 - a. ≥ 1 blood culture positive for yeast or *Candida*
OR
 - b. Positive test for *Candida* from a Sponsor-approved rapid IVD
OR
 - c. Positive gram stain (or other method of direct microscopy) for yeast or positive culture for *Candida* spp. from a specimen obtained from a normally sterile site.
4. Presence of one or more systemic signs attributable to candidemia or invasive candidiasis (e.g., fever, hypothermia, hypotension, tachycardia, tachypnea, local signs of inflammation) appearing from ≤ 12 hours prior to the qualifying positive culture through time of randomization.
5. Willing to initiate or continue medical treatment to cure infections, including receipt of antibiotics and surgical procedures, if required. Patients receiving only medications and measures for comfort and not cure should not be enrolled.
6. Female subjects of childbearing potential (all female subjects between 18 years and < 2 years post-menopausal unless surgically sterile) must agree to and comply with using one barrier method (e.g., female condom with spermicide) plus one other highly effective method of birth control (e.g., oral contraceptive, implant, injectable, indwelling intrauterine device, vasectomized partner), or sexual abstinence (only possible if it corresponds to the subject's usual lifestyle) while participating in this study and at least 30 days from the last dose of study drug. Male subjects must be vasectomized, abstain from sexual intercourse, or agree to use barrier contraception (condom with spermicide), and also agree not to donate sperm while participating in the study and for 90 days thereafter (and at least 120 days from the last dose of study drug).
7. For candidemia only subjects, drawing of a set of blood cultures within 12 hours prior to randomization in the study. The result of these blood cultures is not required for inclusion in the study.

7.1.1 Rapid In Vitro Diagnostics for Candidemia and Invasive Candidiasis

The addition of rapid IVD for the identification of subjects with candidemia and/or invasive candidiasis is being employed to reduce the amount of prior empiric antifungal therapy being administered to potential study subjects. Rapid IVDs for *Candida* spp. used for inclusion in this study must be approved by the Sponsor prior to use in the study. Currently approved rapid IVDs include the T2Candida Panel (T2 Biosystems) and the Septifast polymerase chain reaction (PCR) test (Roche). Subjects may be enrolled based on a positive result from a Sponsor-approved rapid IVD, but a culture from blood or normally sterile tissue or fluid that is positive for *Candida* spp. will still be the required objective measure for candidemia or invasive candidiasis in the study analyses for efficacy.

Potential subjects with 1 or more risk factors for candidemia and invasive candidiasis should have a Sponsor-approved rapid IVD for *Candida* spp. performed only if the site is drawing a blood sample for blood culture and if empiric antifungal therapy for candidiasis has been administered or will be administered within the subsequent day. Risk factors for candidemia and invasive candidiasis include (but are not limited to):

- Immunosuppression
- Central venous catheter
- Recent abdominal surgery
- Pancreatitis
- End stage renal disease
- Current daily administration of total parenteral nutrition
- Systemic inflammatory response syndrome while on broad spectrum antibiotics

Sites may choose to perform a sponsor-approved rapid IVD in potential subjects without the listed risk factors for candidemia and invasive candidiasis, but the potential subject still must have a blood culture drawn and empiric antifungal therapy administered. A call to the Medical Monitor is recommended for any questions about risk factors for candidemia and the appropriate subjects on which to perform a rapid IVD for *Candida* spp.

7.1.2 Systemic Signs of Candidemia and Invasive Candidiasis

It is a requirement that at least 1 systemic sign attributable to candidemia and/or invasive candidiasis be present at Screening for the subject to be eligible for enrollment. The Screening period for assessing systemic signs for inclusion in the study may include the 12 hours prior to the collection of the qualifying positive culture when systemic signs of infection were the reason for specimen collection (blood culture or fluid from a sterile site culture or qualifying rapid IVD [e.g., T2Candida Panel]) through study randomization. The possible signs of infection that might be attributable to candidemia and/or invasive candidiasis at baseline include fever, hypothermia,

hypotension, tachycardia, tachypnea, and local signs of inflammation (erythema, edema, heat, and pain at the site of the qualifying blood culture).

For the listed systemic signs of candidemia, the qualifying parameters are provided below:

Systemic Sign of Candidemia	Qualifying Parameters
Fever	Oral or axillary temperature $\geq 38^{\circ}\text{C}$ (100.4°F) or a tympanic, temporal, rectal, or core body temperature $\geq 38.3^{\circ}\text{C}$ (101°F)
Hypothermia	Tympanic, temporal, rectal, or core body temperature $\leq 35^{\circ}\text{C}$ (95.2°F)
Hypotension	Systolic blood pressure < 90 mm Hg or mean arterial pressure < 70 mm Hg with a normovolemic or hypervolemic status
Tachycardia	Heart rate > 100 beats per minute with a normovolemic or hypervolemic status
Tachypnea	Respiratory rate > 20 breaths per minute
Local Signs of Inflammation	Erythema (rubor), edema (tumor), heat (calor), and pain (dolor) at the site of infection

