13.1 Analysis Populations

The analysis populations are defined for this study as follows:

- The intent-to-treat (ITT) population will include all randomized subjects, regardless of whether the subject receives study drug.
- The Safety population will include all subjects who received any amount of study drug.
- The mITT population will include all subjects who had documented *Candida* infection based on Central Laboratory evaluation of a culture from blood or another normally sterile site obtained ≤ 4 days (96 hours) before randomization and received ≥ 1 dose of study drug.
- The clinically evaluable (CE) population will include all subjects in the mITT population who also met inclusion criterion #4, did not meet exclusion criteria #1, #2, or #5, had an assessment of both mycological and clinical response at Day 14 in the window of Day 14 (± 1 day) (subjects with invasive candidiasis documented by radiologic/imaging evidence also must have an assessment of radiologic response), and did not have any other factor that could confound the assessment of the global response at Day 14.
- PK Analysis Population will include all Rezafungin for Injection subjects with at least 1 plasma sample obtained for PK analysis.

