2.3. Exploratory Efficacy Outcomes

2.3.1. Resolution of Attributable Systemic Signs of Candidemia and/or Invasive Candidiasis that were Present at Baseline

It is a requirement that at least 1 systemic sign attributable to candidemia and/or IC be present at Screening for the subject to be eligible for enrollment. The Screening period for assessing systemic signs for inclusion in the study may include the 12 hours prior to the drawing of the qualifying positive culture (when systemic signs of infection resulted in obtaining blood cultures), qualifying positive culture from a sterile site, or qualifying rapid in vitro diagnostic, through enrollment. The possible signs of infection that might be attributable to candidemia and/or IC at baseline include fever, hypothermia, hypotension, tachycardia, tachypnea, and local signs of inflammation.

For the listed systemic signs of candidemia, the qualifying parameters are listed below:

Fever: Oral or axillary temperature $\geq 38^{\circ}\text{C}$ [100.4°F] or a tympanic, temporal, rectal, or core body temperature $\geq 38.3^{\circ}\text{C}$ [101°F]

Hypothermia: Tympanic, temporal, rectal, or core body temperature $\leq 35^{\circ}\text{C}$ [95.2°F]

Hypotension: Systolic blood pressure < 90 mmHg or mean arterial pressure < 70 mmHg with a normovolemic or hypervolemic status

Tachycardia: Heart rate > 100 beats per minute with a normovolemic or hypervolemic status

Tachypnea: Respiratory rate > 20 breaths per minute

Local signs of inflammation: Erythema, edema, heat and pain at the site of the qualifying culture

Resolutions of systemic signs will be programmatically categorized as follows:

- Yes (resolution): Resolution of all attributable systemic signs of candidemia and/or invasive candidiasis that were present at baseline and no new attributable systemic signs that were not present at baseline
- No (not resolved): New attributable systemic signs that were not present at baseline or lack of resolution of any attributable systemic signs of candidemia and/or invasive candidiasis that were present at baseline

Subjects whose assessment of systemic signs was not completed at a visit or at baseline for any reason (including death) will not be included in the analysis.

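### The hypothermia criterion pairs 35 °C with 95.2 °F, but these are different temperatures, so the two printed limits disagree for readings of 95.1 to 95.2 °F

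*Protocol*

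**What the plan says.** The table of qualifying parameters in Protocol 7.1.2 sets hypothermia, for tympanic, temporal, rectal or core measurement, at "core body temperature $\leq 35^{\circ}\text{C}$ (95.2°F"). SAP 2.3.1 carries the same pair: "core body temperature $\leq 35^{\circ}\text{C}$ [95.2°F"]. The fever row of the protocol table gives two further pairs, "Oral or axillary temperature $\geq 38^{\circ}\text{C}$ (100.4°F") and "core body temperature $\geq 38.3^{\circ}\text{C}$ (101°F").

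The sign is used in three places:

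- **Entry.** Protocol 7.1.2 requires "at least 1 systemic sign attributable to candidemia and/or invasive candidiasis be present at Screening for the subject to be eligible for enrollment". Inclusion criterion 4 (Protocol 7.1) asks for "Presence of one or more systemic signs attributable to candidemia or invasive candidiasis" and lists hypothermia as one of six examples, without a temperature.
- **CE population.** Protocol 13.1 restricts it to "all subjects in the mITT population who also met inclusion criterion #4", among other conditions, and SAP 2.6 has the same requirement. SAP 4.3.1.1 uses the CE population for the third sensitivity analysis of the EMA primary outcome.
- **Exploratory outcome.** SAP 2.3.1 states "Resolutions of systemic signs will be programmatically categorized as follows" and then defines resolved and not resolved in terms of attributable signs, in the section that prints the temperature pair.

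Neither document states which unit prevails if the two figures conflict.

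**The concern.** A threshold printed in two units should classify every reading the same way. If the figures differ, a reading between them shows the sign as present in one unit and absent in the other. Here the threshold is an operating definition and not background text: it can decide whether a subject has a qualifying sign, whether inclusion criterion 4 was met when CE membership is assigned, and possibly whether a sign counts as resolved at a later visit. The pair is the same in both documents, so neither can be used to correct the other.

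**Working it through.** **Inputs.** Hypothermia: 35 °C and 95.2 °F (Protocol 7.1.2 and SAP 2.3.1). Fever: 38 °C and 100.4 °F, and 38.3 °C and 101 °F (Protocol 7.1.2), used as a check on the document's own conversions.

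**Formulas.** F = C × 9/5 + 32 and C = (F − 32) × 5/9.

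**Step 1: try to reproduce the printed figure.**

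- 35 × 9/5 + 32 = 95.0 °F, exactly. Rounding to a tenth or to a whole degree does not give 95.2.
- (95.2 − 32) × 5/9 = 35.11 °C.
- 35.1 × 9/5 + 32 = 95.18 °F, which rounds to 95.2. The printed Fahrenheit figure therefore matches 35.1 °C and not 35 °C.
- Gap between the two limits: 95.2 − 95.0 = 0.2 °F, or 35.11 − 35.00 = 0.11 °C.

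**Step 2: check the fever pairs.**

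- 38 × 9/5 + 32 = 100.4 °F, as printed.
- 38.3 × 9/5 + 32 = 100.94 °F, printed as 101, which is right to the nearest degree. The gap is 101 − 100.94 = 0.06 °F. On a 0.1 °F scale the two fever limits still agree: 100.9 °F (38.28 °C) fails both and 101.0 °F (38.33 °C) meets both.

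**Step 3: find the readings on which the hypothermia limits disagree**, assuming readings to 0.1 of a degree.

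| Reading | Converted | At or below 35 °C? | At or below 95.2 °F? |
|---|---|---|---|
| 95.0 °F | 35.00 °C | yes | yes |
| 95.1 °F | 35.06 °C | no | yes |
| 95.2 °F | 35.11 °C | no | yes |
| 95.3 °F | 35.17 °C | no | no |
| 35.0 °C | 95.00 °F | yes | yes |
| 35.1 °C | 95.18 °F | no | yes |
| 35.2 °C | 95.36 °F | no | no |

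The conflict is confined to 95.1 and 95.2 °F, and to a 35.1 °C reading if someone converts it and applies the Fahrenheit figure.

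**Step 4: trace the consequence.** One attributable sign is enough for inclusion criterion 4. For entry or CE status to change, three things must hold together: the reading lies in the band, the Fahrenheit figure is the one applied, and no other attributable sign is present. For sign resolution, a reading in the band would have to be classified by the Fahrenheit figure, and the sign would also have to be judged attributable. The mITT definition (Protocol 13.1, SAP 2.6) does not refer to inclusion criterion 4.

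**The case against.** The arithmetic is not open to dispute, and because the pair appears in both documents it is not an extraction fault. The case on the other side is that almost nothing follows from it.

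- **Celsius is the working unit elsewhere.** The APACHE II table (Protocol Appendix 5) scores temperature in Celsius. SAP 4.5.3 adjusts for measurement method in Celsius and sets its potentially clinically significant limits in Celsius only. In both affected sections Fahrenheit is the bracketed figure. This makes a conflict in the analysis less likely, but no sentence says that Celsius governs.
- **A reader might infer that entry and CE membership depend generally on the thermometer used.** They do not. Five other signs can qualify a subject, and the documents do not say that any site records in Fahrenheit.
- **A reader might infer that clinical cure, and through it the EMA primary outcome, is affected.** The documents do not show this. Clinical response (Protocol 10.2.2, SAP 2.2.3) is the Investigator's judgement on resolution of attributable signs and symptoms, with no numeric limit, and Protocol 7.1.2 presents its figures as qualifying parameters for Screening.
- **A reader might infer that the programmed resolution outcome will give two answers.** That is possible but not shown. Sites assess the presence or absence of signs (Protocol Table 1) and the Investigator decides attribution (SAP 4.1.6), which a temperature alone cannot supply. Some ambiguity remains, because SAP 2.3.1 prints the pair beside the resolution rule.
- **A reader might infer that 95.2 °F is simply a faulty conversion and that 35 °C is the intended limit.** The documents do not settle this, since 95.2 °F is what 35.1 °C rounds to.
- **Timing.** Randomization for primary enrollment ended on Aug 16, 2021 (SAP 1.2.2), before SAP V4.0 of 02 November 2021 (SAP Appendix 9). A correction cannot change who entered then. It still bears on how the sign is classified in analysis and on the extended enrollment in China.

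**Conclusion.** The point holds as an inconsistency within one definition. The two printed limits are 0.2 °F (0.11 °C) apart, rounding does not explain the gap, and they classify readings of 95.1 to 95.2 °F differently.

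The consequence is very small. Entry and CE status can change only for a subject in that band who is judged in Fahrenheit and has no other attributable sign. The CE population serves one EMA sensitivity analysis. The exploratory sign-resolution outcome could be affected in the same band, subject to attribution. The mITT rule, power and alpha are unaffected, so the primary analyses could be touched only through who was enrolled. No effect on clinical cure is shown.

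This rests on readings being taken to 0.1 of a degree and on at least one site or program using the Fahrenheit figure. The documents give neither the recording unit nor the number of subjects in the band, so no count can be estimated. If all temperatures are held in Celsius and only the 35 °C figure is programmed, the effect is limited to what sites apply at the bedside.

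**What to change.** Reconcile the Celsius and Fahrenheit figures in Protocol 7.1.2 and SAP 2.3.1 so that they are exact equivalents, and state in both places which unit governs wherever the sign is classified. Which limit was intended is for the sponsor to confirm, because the documents do not show it.

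Leave the Investigator's attribution of signs as it is. Deriving the sign from temperature alone would bypass that attribution and would be a larger change than this inconsistency calls for.

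The cost is one corrected figure and one added sentence in each document. If any program applies a temperature cut-off for this sign, it should be checked against the stated unit. Sample size and the planned analyses do not change.
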